5. STATISTICAL METHODOLOGY

5.1 Statistical Methods

All data will be presented by treatment group as well as for the whole sample.

For all baseline, demographic and efficacy variables, data will be summarized and analyzed by randomized treatment group as per ITT.

In summary tables of normally distributed continuous variables, the following descriptive statistics will be used: minimum and maximum, mean, and standard deviation (SD). In summary tables of non-normally distributed variables data will be presented using the minimum, maximum, median and lower and upper quartiles.

In summary tables of categorical variables, counts and percentages will be used. The denominator for each percentage will be the number of patients within the randomization group unless otherwise specified.

Rates of events will be calculated as the ratio of the total number of events recorded divided by the total patient-time in study (months or days). Total patient-time will be

calculated by summing the time (in days) that patients were at risk for a specific event from the time they were randomized in the study until study exit. Rates and 95% confidence intervals will be reported.

For any variable measured at multiple points in time, change from baseline will be calculated as the difference between the value of the variable at a specific point in time (e.g. 5 weeks) minus the baseline value.

Relative change from baseline will be calculated as the value of a parameter at a specific point in time minus the baseline value of the parameter divided by the baseline value of the parameter.

Percent change will be calculated as the relative change multiplied by 100.

Hypothesis testing will be conducted at the 0.05 two-sided significance level for the primary endpoint. No formal hypothesis tests will be conducted for the secondary endpoints, rather, we will calculate estimates and 95% confidence intervals by group.

P-values will be rounded to three decimal places. P-values less than 0.001 will be reported as <0.001 in tables. P-values greater than 0.999 will be reported as >0.999.

Should any of the statistical methods proposed prove unsuitable during data analysis, more appropriate methods will be used. These include data transformation (for example to a logarithmic scale) to satisfy model assumptions such as normally distributed residuals with constant variance, or the application of non-parametric techniques.

Additional ad-hoc analyses may be conducted as deemed appropriate.

All statistical analysis will be performed using SAS V9.4 or higher.

5.2 Handling of Dropouts and Missing Data

Missing baseline values that are needed to compute absolute, relative, or percent change from baseline will be imputed using mean imputation (Thompson, 2005). The missing values of a variable will be replaced with the observed sample mean of that variable. Mean imputation is appropriate because baseline variables are independent of randomization assignment.

5.2.1 Missing values for the primary outcome

Missing outcome values for primary endpoint analysis will not be imputed. For the primary endpoint, missing data can be the result of patient refusal, missed visit, or study dropout (withdrawal, lost to follow-up). Missing data due to patient refusal or missed visits are assumed to be missing at random (MAR). Study dropout is also assumed to be MAR.

5.2.2 Missing values for the secondary outcomes

Missing outcome values for secondary endpoints will not be imputed.

5.2.3 Sensitivity analysis

Sensitivity analyses will be conducted to investigate possible violations of the missing at random assumption. Specifically, we will determine if patients missing the primary outcome fMRI differ from patients with fMRI data at V5 in terms of:

- Baseline demographics
- Baseline rewards circuit activation
- Longitudinal anhedonia symptoms
- Longitudinal depression symptoms
- Treatment group

Three imputed datasets will be created to assess the robustness of the primary endpoint analysis:

- Multiple imputation will be used to impute any missing V5 value of the bilateral VS activation
- Lowest overall observed (across both treatment groups) of the bilateral VS activation will be imputed for any missing V5 value
- Highest overall observed (across both treatment groups) of the bilateral VS activation will be imputed for any missing V5 value

In addition, we will conduct sensitivity analyses to examine the effect of lowering the dose of ezogabine in patients who could not tolerate the protocol-defined maximum dosage. Specifically, we will determine if patients on a reduced dose compared to the protocol-defined dose differed in terms of

- Baseline demographics
- Baseline rewards circuit activation
- Longitudinal anhedonia symptoms
- Longitudinal depression symptoms

We will repeat the primary endpoint analyses in the subset of patients treated per-protocol and compare primary endpoint results between patients on a reduced dose versus the protocol-defined maximum dose.

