16 STATISTICAL METHODS AND CONSIDERATIONS

The Statistical Analysis Plan (SAP) will contain any modification to the analysis plan described below, and in the case of a discrepancy between the protocol and the SAP, all analyses will be performed according to the SAP. Any modifications will be made prior to the unblinding of study data.

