16.1 Data set analyzed

Data will be analyzed on an intent-to-treat basis, i.e., patients will be analyzed according to the treatment assigned by randomization regardless of the treatment actually received. Patients missing the follow up fMRI will be excluded from the primary outcome analysis. As it is impossible to test the missingness mechanism and data may not be missing completely at random, a secondary sensitivity analysis will be conducted using multiple imputation for the primary endpoint to investigate possible violations of the missing at random assumption. Extreme case imputation, whereby the lowest and highest overall observed values for the primary endpoint are imputed for any missing value, will also be used to assess the robustness of the primary endpoint analysis.

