3. EFFICACY ENDPOINTS

3.1 Primary Endpoint

The primary endpoint of this study is the baseline-corrected fMRI activation in an a priori bilateral ventral striatum (VS) area mask during the “gain” cue of the Incentive Flanker Task (IFT) contrasted with neutral cue for reward anticipation. The primary outcome fMRI will be obtained at 5 weeks post-randomization. The primary endpoint will be used as the sole criterion for the “go-no go” decision.

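### The SAP's lowest/highest imputation gives both arms the same value, so the pair need not bracket the result under informative dropout; arm-specific delta shifts would

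*SAP*

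**What the plan says.** The primary analysis leaves missing week-5 (V5) scans unimputed and treats refusals, missed visits and withdrawals as MAR (SAP 5.2.1: "Study dropout is also assumed to be MAR"). SAP 5.2.3 then gives sensitivity analyses whose declared aim is to look for departures from MAR. They have two parts.

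- A comparison of patients with and without the V5 scan on baseline demographics, baseline activation, the course of anhedonia and depression, and treatment group.
- "Three imputed datasets will be created to assess the robustness of the primary endpoint analysis". The first: "Multiple imputation will be used to impute any missing V5 value of the bilateral VS activation". The second: "Lowest overall observed (across both treatment groups) of the bilateral VS activation will be imputed for any missing V5 value". The third: "Highest overall observed (across both treatment groups) of the bilateral VS activation will be imputed for any missing V5 value".

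Protocol 16.1 has the same extreme-value rule and the same purpose for the imputation: "a secondary sensitivity analysis will be conducted using multiple imputation for the primary endpoint to investigate possible violations of the missing at random assumption". Neither document states an imputation model, a shift away from MAR, a tipping-point analysis or an extreme-case rule that differs by arm. SAP 5.3.1 adds withdrawals and their main reasons by arm.

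**The concern.** A lowest/highest pair looks like a worst case and a best case for the treatment effect. It would be that only if the arms were pushed in opposite directions. Here both arms are pushed in the same direction by the same value, so much of the push cancels in the difference between arms, and all of it cancels when losses are equal. A reader who sees the two datasets agree may take the result to be insensitive to missing scans, when the agreement comes from the construction.

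This matters because of the weight on this one result (SAP 3.1: "The primary endpoint will be used as the sole criterion for the" go/no-go decision), with 48 patients and no replacement of withdrawals (Protocol 12.3). The useful question is how much lower the unseen ezogabine activations would have to be before the conclusion changed. The planned datasets do not answer it.

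**Working it through.** **Inputs.** From the documents: 24 per arm, effect 0.8 SD, correlation 0.6 between the two scans, two-sided 0.05 (Protocol synopsis and 16.6; SAP 5.1 and 5.4.1). All missing counts are assumptions, because no dropout rate is given.

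**Step 1: the plan's own figure.** The SD of change is sqrt(2 × (1 − 0.6)) = 0.894. A two-sample t comparison with 24 per arm and a difference of 0.8 has 85.8% power, against the stated 85%. It reproduces, so the calculations below use this scale.

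**Step 2: algebra.** Let mE and mP be the missing fractions in the ezogabine and placebo arms, and V the single imputed value. In expectation, with scans lost at random,

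estimate = true effect + (mE − mP) × (V − placebo mean) − mE × true effect.

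The last term is the forced zero effect among missing patients. V enters only through mE − mP, so

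- planned gap, highest minus lowest = |difference in missing counts| / 24 × observed range;
- arm-opposed gap = (sum of missing counts) / 24 × observed range.

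With 4 missing per arm the observed range averages about 4.64 SD, so each one-patient difference opens about 4.64 / 24 = 0.19 SD. The cancellation holds whether V is the V5 value or the change.

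**Step 3: numbers.** Mean estimates in SD units from 20,000 simulated trials per row, true effect 0.8, scans lost at random:

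| Missing (ezogabine, placebo) | Lowest | Highest | Arm-opposed range | Planned width / opposed width |
|---|---|---|---|---|
| 2, 2 | 0.73 | 0.73 | 0.34 to 1.13 | 0 |
| 4, 4 | 0.67 | 0.67 | −0.11 to 1.44 | 0 |
| 5, 4 | 0.56 | 0.75 | −0.22 to 1.52 | 1/9 |
| 6, 2 | 0.28 | 1.05 | −0.11 to 1.44 | 1/2 |
| 4, 0 | 0.33 | 1.12 | 0.33 to 1.12 | 1 |

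Hand checks: for 4 and 4, 0.8 − (4/24)(0.8) = 0.667. For 6 and 2 with a mean lowest value of −1.95, 0.8 + (4/24)(−1.95) − (6/24)(0.8) = 0.275.

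**Step 4: response to informative loss.** Suppose 4 scans are missing per arm and the unseen ezogabine values are truly 2 SD lower (an illustrative figure). The full-sample effect is 0.8 − (4/24)(2) = 0.47. Both planned datasets still average 0.67, because nothing in them depends on the unseen values.

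**Step 5: how often this bites.** Take independent loss at the same rate in both arms, between 1 in 12 and 1 in 3, with at least one scan missing. Counts are then exactly equal in 20% down to 12% of trials, and the planned width averages 0.43 down to 0.17 of the arm-opposed width. With 1 in 4 lost on ezogabine and 1 in 12 on placebo, counts are equal in about 4% and the mean ratio is 0.53.

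**Step 6: what a delta analysis gives.** Multiple imputation of V5 from baseline within arm, with missing ezogabine scans shifted by −1 SD, averages 0.64 with 4 missing per arm (0.8 − 4/24 = 0.63) and 0.55 with 6 and 2 missing. With 4 per arm, the median shift at which significance is lost is −1.6 SD (interquartile range −2.3 to −0.9), among trials significant without a shift.

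**The case against.** The strongest reply is that the plan is open, pre-specified and already severe. With 4 missing per arm at random and a true 0.8 SD effect, 79% of trials are significant on completers but only 39% on either planned dataset; with 2 per arm it is 82% and 61%. A −1 SD shift would be gentler: 55% significant with 4 per arm, and 44% against 5% for the planned lowest dataset with 6 and 2 missing. A reader might therefore infer that robustness goes untested, and the documents do not support that. What stands is that the severity is of the wrong kind. With equal loss it comes from pulling the effect towards zero and inflating the variance, not from any stated assumption about the patients who were lost.

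A reader might also infer that the pair usually collapses to one number. It does not. Exact equality is uncommon (step 5), and 5 and 4 missing already gives 0.56 and 0.75. Loss concentrated on ezogabine is plausible given the side effects listed in Protocol 1.2, and there the pair does respond.

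Nor do the protocol and SAP conflict on the purpose of multiple imputation. Both place it under the aim of probing MAR, so the rule giving the SAP precedence is not needed. Calling it a MAR analysis is an inference from its standard form. If the unstated model used the weekly symptom scores, its MAR assumption would be weaker than that of the primary analysis, but still MAR.

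The planned comparison of patients with and without scans, and the withdrawals by arm, would show whether loss is unbalanced or selective. They do not turn that into an effect on the estimate.

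Finally, few scans may be lost. Patients who cannot tolerate an increase can stay in the study to V5 (Protocol 8.4.1), V5 procedures can be repeated within the window (10.4), and early withdrawals before V5 are scanned (10.6).

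**Conclusion.** The point holds as a limited one. The lowest and highest datasets force a zero effect among missing patients and differ by |difference in missing counts| / 24 × the observed range. They match the arm-opposed bounds only when all loss is in one arm. In other cases they do not generally bracket the result under informative dropout, and their agreement should not be read as robustness. The algebra is exact. The sizes rest on 24 per arm, 0.8 SD, correlation 0.6, normal data and assumed missing counts. If very few scans are lost, the practical effect is small.

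It does not follow that the primary analysis is wrong or that the planned datasets should be dropped. This is a low-priority, inexpensive improvement.

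**What to change.** Keep the three planned datasets and make these changes to SAP 5.2.3 before unblinding.

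- State the imputation model, and label standard multiple imputation as a MAR analysis.
- Add delta-adjusted multiple imputation with shifts varied separately by arm over a grid fixed in advance. For example, shift missing ezogabine scans from 0 to −2 SD with placebo unshifted, then exchange the arms. State the sign of each shift, since lowering missing placebo scans favours ezogabine.
- Report the delta at which the primary conclusion changes, or that it does not change within the grid.
- Show arm-opposed extremes, if wanted, as outer bounds only. They are unsuitable as a pass/fail test: under a true 0.8 SD effect the adverse bound is significant in about 10% of trials with 2 missing per arm and about 0.2% with 4.

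The cost is a short SAP paragraph and some SAS code, with no new data. The downside is a little extra analysis, and wide bounds if many scans are missing.

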5.3 Patient Characteristics

5.3.1 Patient Disposition

The subject disposition table will summarize patients' characteristics by randomization group and overall.

- The number (%) of patients randomized
- The number (%) of patients withdrawn or lost to follow-up by the primary outcome visit (week 5)

The number (%) of subjects who complete and withdraw/lost to follow-up from the study and the primary reason for withdrawal will be summarized by randomization group and

overall for all subjects.

The percentages will be calculated based on the total number of patients randomized in each randomization group.

5.3.2 Protocol Deviations

Major and minor protocol deviations are defined as deviations from the procedures outlined in the protocol. All statistical analyses and summaries will be conducted on an intent-to-treat basis (with the exception of the sensitivity analysis to examine the effect of dose reduction due to medication intolerance).

Treatment compliance will be compared by treatment group with compliance defined as the number (%) of total prescribed pills taken, and subject report will be compared to serum drug levels.

5.3.3 Demographic Characteristics

Demographic and baseline characteristics data including age, gender, race, and ethnicity will be summarized using summary statistics for continuous variables or by group frequencies and percentages for categorical variables, as appropriate.

5.4 Efficacy Analysis

5.4.1 Analysis of Primary Endpoint and Determination of Sample Size

The primary endpoint is the change in activation of the bilateral VS, a region of the rewards circuit in the brain, at 5 weeks from randomization. Activation will be measured by fMRI, and beta weights for each subject will be calculated to create a contrast between gain and neutral cues to model reward anticipation as described in the Neuroimaging Methods section of the protocol. To calculate the beta weight for the bilateral VS, the beta weights for the right and left VS will be averaged.

A linear mixed effects model with a single random intercept term will be used to assess the change in activation of the bilateral VS by treatment group. A sample size of 48 provides 85% power to detect a difference in means between groups of 0.8 standard deviations assuming a correlation of 0.6 between a pair of measurements made on the same subject using a two-sided 0.05 significance level test.

Although randomization is stratified by site, the primary endpoint analysis will be of the pooled dataset; secondary analyses will provide site-specific estimates.

No adjustment to the primary analysis will be made for baseline measures that are found to be imbalanced but, if applicable, secondary sensitivity analyses may adjust for any factors that are imbalanced at a significance level below $p = 0.05$. (Altman, 1985) (Peter Peduzzi, 2002) (Senn, 1989) (Senn, Testing for baseline balance in clinical trials, 1993)

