16.4 Analysis of Secondary Endpoint

Change in activation of other regions of the cortico-striatal rewards circuit in the brain, namely the bilateral dorsal striatum (DS), mPFC, and ACC, will be analyzed in the same manner as the primary endpoint.

The performance of the PRT and the clinical and self-reports will be examined by using descriptive statistics such as the mean, standard deviation, median and interquartile range for continuous measures, and by frequency distributions for categorical variables.

Safety and tolerability data will be summarized by treatment group. Adverse event rates will be coded by body system and MedDra classification term. Adverse events will be tabulated by treatment group and will include the number of patients for whom the event occurred, the rate of occurrence, and the severity and relationship to study drug. Incidence of adverse events will be compared between treatment groups using Poisson regression.

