1.2.2 Randomization and masking

Patients will be randomized in a 1:1 allocation to ezogabine or placebo. Randomization will be stratified by center balanced by randomly permuted blocks, and treatment code will be allocated through the interactive web response system (IWRS). Randomization will take place only after it has been determined that all study eligibility criteria have been met and the baseline fMRI scan has been obtained.

This is a double-blind, placebo-controlled trial. Site personnel and patients will be blinded to treatment assignment throughout the trial.

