5.4.2 Secondary Endpoints

All secondary analyses will be performed using the ITT population.

As the secondary fMRI outcomes are exploratory analyses, we will present the mean and 95% confidence interval of the difference in change in activation between treatment groups rather than conducting formal hypothesis testing. As with the bilateral VS, a single beta weight for the bilateral DS will be calculated by averaging the beta weights for the left DS and right DS.

Linear mixed effects models will be used to analyze the anhedonia, depression, and general functioning scales that are collected at multiple time points. Slopes will be estimated with 95% confidence intervals by treatment group. Mean change and 95% confidence intervals by group will be presented for measures collected at baseline and primary outcome only.

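### The primary model's fixed effects are not listed; it appears to compare raw change in VS activation, and adjusting for the baseline scan would be more efficient (about 92% against 86% power under the plan's own assumptions)

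*SAP*

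**What the plan says.** The endpoint is the change in bilateral VS activation (gain cue minus neutral cue) from baseline to week 5. SAP 5.4.1 and Protocol 16.3 give the same model: "A linear mixed effects model with a single random intercept term will be used to assess the change in activation of the bilateral VS". Neither lists the fixed effects.

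Four other places bear on what will be fitted:

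- SAP 5.1: "change from baseline will be calculated as the difference between the value of the variable at a specific point in time" and the baseline value.
- Protocol 16.4: the other reward regions "will be analyzed in the same manner as the primary endpoint". SAP 5.4.2 reports those regions as "the difference in change in activation between treatment groups".
- SAP 5.4.1, sample size: 48 patients give "85% power to detect a difference in means between groups of 0.8 standard deviations assuming a correlation of 0.6 between a pair of measurements" on the same subject, at a two-sided 0.05 level.
- SAP 5.4.1, covariates: "No adjustment to the primary analysis will be made for baseline measures that are found to be imbalanced". Sensitivity analyses may adjust for factors that differ at p below 0.05.

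SAP 1.2.2 allows randomisation only once eligibility is confirmed and "the baseline fMRI scan has been obtained". On the role of the endpoint, SAP 3.1 says: "The primary endpoint will be used as the sole criterion for the" go/no-go decision. Protocol 2.1 and 3.1 also require acceptable tolerability.

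**The concern.** If the model contains treatment, visit and their interaction with a random intercept, then with two scans per patient it is simply a comparison of mean change between arms. Subtracting the whole baseline value is the most efficient use of it only when the regression slope of V5 on baseline is 1. At a correlation of 0.6 with equal SDs the slope is 0.6, so subtraction overcorrects and carries extra baseline noise into the comparison.

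What is at stake is precision on the one endpoint that is formally tested. Protocol 2.1 describes a go in terms of both significance and effect size, and a smaller standard error serves both. There is little reserve. No dropout allowance is stated, patients without a follow-up scan are excluded from the primary analysis (Protocol 16.1), and withdrawn patients are not replaced (Protocol 12.3). The scan offered at early withdrawal (Protocol 10.6) recovers some of these patients, so a withdrawal is not always a lost scan.

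**Working it through.** **Inputs from the documents.** N = 48, 24 per arm; difference 0.8 SD; correlation r = 0.6; two-sided alpha 0.05 (SAP 5.4.1 and 5.1, Protocol 16.6). A single SD is quoted, so equal SDs at both visits are implied.

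**Step 1: reproduce the 85%.** The SD of change is √(2(1 − 0.6)) = √0.80 = 0.894, so the standardised difference is 0.8/0.894 = 0.894. A noncentral t with 46 df gives **85.8%**, which matches. Alternatives do not match: follow-up value only, 77.4%; baseline-adjusted, about 92%.

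**Step 2: confirm what the two-visit model does.** A random-intercept model with group, visit and group-by-visit was fitted to simulated complete data. It gave the same estimate and standard error as the change-score comparison (0.926 and 0.296 by both routes in one dataset).

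**Step 3: adjust for baseline.** The residual variance of V5 given baseline is 1 − r² = 0.64, against 0.80 for raw change. The ratio is (1 + r)/2 = 0.80, a 20% cut. The standardised difference becomes 0.8/0.8 = 1.0. With 45 df, and the noncentrality reduced for chance baseline imbalance and averaged over random baselines, power is **91.8%** (92.4% without that reduction). In 40,000 simulated trials, power was 86.0% for raw change and 91.9% adjusted, with type I error of 5.1% and 4.9%.

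**Step 4: precision at N = 48.**

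- Raw change: SE = √(0.80 × 2/24) = 0.258 SD; 95% half-width 2.013 × 0.258 = 0.52 SD.
- Adjusted: SE = √(0.64 × 2/24 × (1 + 1/44)) = 0.234 SD; half-width 2.014 × 0.234 = 0.47 SD.

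Raw change would need about 58 patients to reach 91.7%.

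**Step 5: vary what the plan does not fix.** The evaluable numbers, the other correlations and the SD ratios are assumptions. For unequal SDs, with the V5 SD equal to k times baseline, the variances are 1 + k² − 1.2k (raw) and 0.64k² (adjusted), and the effect stays at 0.8 baseline SD. At k = 1.3 these are 1.13 and 1.08.

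| Case | Raw change | Adjusted |
|---|---|---|
| r = 0.6, 48 scans | 85.8% | 91.8% |
| r = 0.6, 46 scans | 84.3% | 90.6% |
| r = 0.6, 44 scans | 82.6% | 89.2% |
| r = 0.6, 40 scans | 78.7% | 85.9% |
| r = 0.4, 48 scans | 69.7% | 83.3% |
| r = 0.5, 48 scans | 77.4% | 87.2% |
| r = 0.7, 48 scans | 93.9% | 96.4% |
| r = 0.6, V5 SD 1.3 × baseline | 72.3% | 73.0% |
| r = 0.6, V5 SD 0.8 × baseline | 90.8% | 98.7% |

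**Step 6: check the other way of using baseline.** A random-intercept model that constrains the two arms to a common baseline mean also recovers precision, but it assumes equal variances at both visits. In simulation under no treatment effect (N = 48, r = 0.6), its type I error was near 5% at equal SDs, about 7% at a V5 SD of 1.2 times baseline, about 8% at 1.3 times, and about 3% at 0.8 times. Raw change and ANCOVA stayed near 5% throughout.

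**The case against.** **The raw-change model is an inference.** Matching 85% to a change-score test shows how N was chosen, not what will be fitted. SAP 3.1 and the protocol synopsis describe the endpoint as corrected for baseline, which fits subtraction or adjustment. A random-intercept model with a common baseline mean would also fit the one-sentence description. This stands: raw change is the likelier reading, but the documented gap is that the fixed effects are not listed.

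**The gain is conditional.** Pilot scans at both time points were available for only six patients (Protocol 1.2), so the correlation and SD ratio are poorly known. This also stands. A reader might take 86% to 92% as a fixed gain; the table shows it is not.

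**Nothing is wrong with the planned analysis.** A reader might infer that it is biased, or that the sample size is miscalculated. The documents support neither: the comparison is valid and the 85% is met with complete data.

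**The SAP may seem to forbid the remedy.** A reader might take "No adjustment to the primary analysis will be made for baseline measures that are found to be imbalanced" as a bar on any baseline covariate. It concerns measures found to differ after randomisation and does not address a prespecified baseline of the outcome. It is loose enough to be misread, so it needs a clarifying clause.

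**The baseline may not always be usable.** The MRI Procedures Appendix lets quality checks flag a scan as needing attention. That is so, but a raw change score needs the same baseline value, and SAP 5.2 already has a mean-imputation rule for missing baselines.

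**Conclusion.** The point holds as one of efficiency and incomplete specification. The most likely primary analysis is a raw change comparison. With the plan's r = 0.6, equal SDs and complete data, baseline adjustment cuts the variance by 20% and raises power from about 86% to about 92%. At the assumed effect, the chance of a non-significant result falls from about 14% to about 8%. Raw change falls just below 85% if two scans are lost, while the adjusted analysis still holds 85% with eight lost; both loss figures are assumptions. The gain is larger at lower correlations, about 2.5 points at 0.7, and under 1 point if the V5 SD is 1.3 times baseline.

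A reader might infer that this endpoint alone settles the go decision. That is the SAP's wording; the protocol adds acceptable tolerability. The change is worth making because it costs almost nothing, not because the planned test is unsound.

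**What to change.** Before unblinding, make these changes in SAP 5.4.1:

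1. Write the primary model out as V5 bilateral VS beta = treatment + baseline VS beta, and test the treatment coefficient.
2. State that the no-adjustment sentence covers measures found to be imbalanced and does not apply to this prespecified covariate.
3. State that the SAP 5.2 rule for missing baselines applies to the covariate.

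Do not substitute a random-intercept model with a common baseline mean unless it allows a separate variance at each visit, because of the type I error shown above. No site term is needed for this purpose.

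The cost is SAP wording and one degree of freedom, with no new data, visits or patients. The opening of Protocol section 16 already lets the SAP modify the analysis before unblinding and gives the SAP precedence.
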